Fidelity: All therapy sessions will be audio recorded and in phase 1 all sessions will be listened to by CIs [name], [name] and [name] and rated using the adapted 10 item checklist which was developed based on the Cognitive Therapy Scale (CTS) which is an 11-item instrument with good reliability when used by experienced clinicians (Young & Beck, 1980), used for a previous SGTS study of CET vs Cognitive Therapy. ([name] et al). In phase 2, 20% of sessions will be randomly selected from early, mid, and late study phases and checked for therapy fidelity.

Baseline differences will be corrected for if required and missing data will be handled by multiple imputation

Sample size and statistical or power issues – Make sure the size and profile of the sample to be recruited is adequate to answer the research question – please provide details:

Phase 2: In our sample size calculations, we assume a correlation between follow-up measures of r 0.7 (Frison & Pocock, 1992). Based on a type I error rate of 5%, power of 90%, two-tailed test, and a VGS standard deviation of 10.2 units ([name] et al., 2010), to detect a significant difference of 8% (i.e. 4.8 points on the scale) in mean VGS scores between the CET and control groups, 50 participants were required in each group. Given the treatment drop-out rate experienced in

the SGTS treatment programme (approximately 35%) we therefore needed to recruit 70 participants in each group of the study giving a total sample size of 140 participants.

How will you measure, manipulate and/or analyse the information collected?

Phase 1 and 2: The primary analysis will use all available data and follow an intent-to-treat principle to investigate any statistically significant differences in primary and secondary outcomes over time between both groups. Secondary analyses will be conducted based on 'as treated' and 'per protocol' approaches within a counterfactual framework using inverse probability weighting (IPW) (Hernan & Hernandez-Diaz, 2012). The IPW uses the inverse of the probability of being in the observed treatment group.

Generalised mixed-effects models will be used in the analysis of repeated measures for primary and secondary continuous and categorical outcomes. Fixed effects (time-invariant variables) in models were intervention group, time in continuous form (intervention period and follow-up), and interaction between group and time.

Finally, the proportion of participants who have VGS scores in the non-problem gambling range (<21) at 2, 6 or 12 month follow-up will be tested using Fisher's exact test.

Effect size statistics will also be produced for comparisons of mean observed scores (Cohen's d) (Cohen, 2013) and associations of nominal variables (Cramer's V or phi for 2 x 2 contingency table) (Cramer, 1946). For nonparametric between-group tests, the Mann-Whitney statistic will be calculated as a measure of effect size (Conroy, 2012).

Phase 1: qualitative data -Semi-structured interviews with purposefully chosen (age above and below 20, those who improved/recovered/those who dropped out/did not recover) 6 intervention participants and 2 therapists to determine recruitment barriers and enablers, acceptability and feasibility and any improvements to the intervention or delivery and recruitment. Of particular interest will be the on-line and social media strategies used to recruit non help seeking sports betters. These interviews will be conducted by the RA using phone or videoconferencing with set open ended questions

Data linkage –what linkages are planned or anticipated?

No data linkage activities are planned.

What impact will a participant withdrawing have on the data and how will this be responded to?

Data already recorded from the participant will be retained (as per ethics requirements) but marked as not for use in the study.

Results, reporting, outcomes and future plans

Post approval monitoring and reporting

Once you have received ethics and governance authorisation for your research project, there are the following mandatory reporting requirements you must adhere to as per The National Statement chapter 5.5:

- Annual review – this is required annually for the life of the research on the anniversary of the approval date.
- Final report – this is required to be submitted on completion of the research.
- Amendments – any change to the approved protocol must be reported to the lead HREC.

Failure to submit the required reports is a breach of the NHRMC Australian Code for the Responsible Conduct of Research R17, R22, the National Statement chapter 5.5 and the terms and conditions of the ethical approval of the study. This failure to submit the required report may result in the ethics approval being withdrawn and the application closed.

The Office for Research has a Research Integrity [webpage](#), which provides the channels in which all SALHN approved studies are monitored, plus self-monitoring tools for our researchers.

Please detail your plans for the return of the research results to the participants:
 
The results of the pilot study will be simply to inform all participants that the data collection and study have been completed and acknowledgement that their contribution is important for preparation for the larger study, For the main study, we will inform the participants of any differences that may occur in between the participants receiving CET and the control intervention controls.

What are your plans for dissemination and publication of project outcomes:
 
Results and a study summary will be provided by local SALHN and Flinders news communications, via local and on-line media and via publications in peer reviewed and open access journals and conference presentations nationally and COVID permitting internationally. No participants will be identifiable in any publication.

Please detail other potential uses of the data at the end of the project:
 
The data itself will have no other use, however the results will be of use clinically to psychiatrists, psychologists and governments with Gambling help services, GPs and Beyond Blue

What are your plans for sharing and/or future use of data and/or follow-up research? i.e. anticipated secondary use of data:
 
The deidentified data may be used by other researchers who wish to try other analytical techniques to possibly improve the classification accuracy

What is the project closure process? I.e. a final report will be submitted to the HREC, where the study data and/or samples will be stored?
 
A final report will be submitted to the ethics committee. The data will be held for the period stipulated by ethics in the secure research data storage repository at Flinders University,

managed by the Flinders University, Information and Digital Services (IDS) department. data files stored in the Universities secure storage facilities (as above) for the stipulated timeframes

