Hypothesis - What is the scientifically valid research question being asked?

Phase 1 pilot: As a pilot study we are not hypothesis testing, instead we are interested in acceptability and feasibility of providing the intervention by phone or videoconferencing instead of face to face. Feasibility is critical in terms of 1) recruitment ie whether we can recruit using on-line ie social media links to sports betting apps, Facebook, Instagram etc to recruit people who are having gambling problems either help-seeking (direct contact to SGTS) or not help-seeking 2) delivery of the intervention CET remotely ie uptake and completion of the therapy program

Phase 2 RCT: CET provided by phone and/or video conferencing will be more efficacious at reducing problem gambling and gambling behaviours including money lost than usual care of education and attention.

Aims - What do the investigators intend to achieve with this research project

Phase 1:

1. To evaluate whether we can use social media advertising to recruit 40 sports betting problem gamblers over 3 months who are either help seeking or not actively help seeking.
- 2 To deliver the CET intervention in up to 10 sessions by phone or video conferencing and determine the acceptability of this approach and the proportion who complete the intervention

Phase 2:

Evaluate whether CET delivered by phone or videoconferencing significantly reduces gambling behaviour compared to usual care of attention and education

Objectives - How will investigators achieve the aims of the research project?

Phase 1:

We will use paid advertising and informal i.e., study initiated social media and contacts with sporting clubs through the SA Office of Problem Gambling to advertise this research study. We have experience of delivering phone and on-line psychological interventions by phone and videoconferencing (HealthDirect) during the COVID pandemic for people presenting the FMC ED in crisis and providing IAPT or MyAPT successfully. We will build on this experience and the use of workbooks to guide a gambler through the treatment program.

Phase 2: to use the learnings from the phase 1 pilot to refine the recruitment of people who have problematic sports betting and deliver a randomised controlled trial nationally to determine if CET is efficacious at reducing gambling behaviour

Expected outcomes - What do the investigators anticipate the outcomes of this research will be?

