Outcomes will be pre - post quantified validated measures of gambling behaviour, anxiety and depression; feasibility and acceptability: ability to recruit people who are sports betting and acceptability of the intervention i.e., number of sessions attended and use of mobile phone and video conferencing to provide therapy. Pre and post outcome data will support existing evidence from our own and others trials to confirm the effect sizes and sample size for a larger phase 2 randomised controlled trial

Phase 2:

Use the learnings and effect size change in the CET group from phase 1 to implement a randomised controlled trial and recruit 140 people who provide consent and baseline data and test the efficacy of the experimental intervention (CET) versus control intervention.

Rationale / justification - How the research will fill any gaps and/or contribute to the field of research or contribute to existing or improved practice?

There are no proven treatments for sports betting internationally. This studies phase 1 and 2 would be the first beyond a case series that would demonstrate pre-post outcome measures to test a highly accessible psychological treatment for sports betting gambling disorder.

Research project setting - i.e. Where is the research being conducted i.e. FMC, GP Plus Marion, Noarlunga Hospital, Tonsley building, Sturt Campus, online forums and alternatives

Please ensure you list the site plus clinic/department / service.

The study will be based at The Flats – Flinders Psychological Therapy Services FMC site from where the therapists will deliver CET and usual care by phone or internet remotely to either SA or whole of Australia. Recruitment will occur for individuals across the whole of SA for phase 1 and all Australia for phase 2.

Methodological approach - clearly describe the specific procedures or techniques that will be used to answer the research question and meet the aims.

The intervention: in the published 6 cases treated by SGTS CET was provided face to face by experienced SGTS staff using a standardised workbook adapted for sports betting. The graded exposure-based approach identifies triggers which elicit a gambling urge and the person then systematically using homework tasks, grades their approach to each trigger until habituation of the gambling urge occurs. Ultimately all urges to gamble are extinguished and the person gains control over their gambling either through abstinence or occasional gambling.

Pilot trial phase 1 (SA)

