
Recruitment: 40 subjects to be recruited over a 3-month period in SA using social media, i.e., Facebook and Instagram to recruit on-line sports betting gamblers and through the OPG Gambling Help Services throughout SA.

Design: this would be a 12-month single arm trial with all participants being offered CET. Participants would receive up to 10 sessions (30-60 mins) provided over 2 months and follow up for another 3 months. We will recruit until we have 40 people who have provided signed consent forms and baseline questionnaires. All will be offered the intervention. As for all psychological interventions, of the 40, a proportion will not attend a single session (~5%), some will attend a single assessment only session (~10%) and others only 1 assessment and 1-2 therapy sessions (~20%) leaving about 65% who attend 4 or more sessions. (ie one assessment + 3 therapy sessions). This provides a naturalistic comparison group ie 35% of the sample who received no or minimal intervention compared to the intervention group (65%) who we will define as having 'an adequate dose' of the intervention. We will also conduct a per

protocol analysis of those who completed all 10 sessions to see the effect of the full dose of the intervention.

Phase 2:

140 subjects will be randomised to intervention (CET) or control ie usual care, in a 2-arm parallel 26 month randomised controlled trial, each arm receiving up to 10 sessions over 12 weeks delivered by phone and/or videoconferencing. Each participant will be followed for 12 months post intervention to determine outcomes of gambling behaviour, problem gambling severity, anxiety, depression and work and social adjustment.

Consumer and Community engagement – investigators are encouraged to consult with [Consumer and Community groups](#) with the design of their research. Please outline any consultation that has occurred.

SGTS has an active consumer group led by [name] a former client of SGTS who has recovered from a gambling addiction. He is employed 0.1FTE by SALHN to provide support to gamblers about to start treatment and during treatment. He has provided input to the design of the workbook and will be asked to continue his current role in contacting participants in the trial during their therapy to provide education and support as well as obtain feedback on the acceptability of the intervention.

What are your outcome measures?

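### Phase 1's named feasibility outcomes cover recruitment and therapy attendance but not return of the VGS, the quantity on which Phase 2's 50 analysable of 70 per group depends

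*Protocol*

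**What the plan says.** The Hypothesis section of the protocol introduces the first Phase 1 feasibility item with "Feasibility is critical in terms of 1) recruitment ie whether we can recruit using on-line ie social media links" and gives the second as "delivery of the intervention CET remotely ie uptake and completion of the therapy program". Phase 1 aim 2 is in the same terms: to "determine the acceptability of this approach and the proportion who complete the intervention". The Expected outcomes section lists "ability to recruit people who are sports betting and acceptability of the intervention i.e., number of sessions attended and use of mobile phone", together with video contact. None of these is the proportion of enrolled people who return the primary outcome.

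Expected outcomes also says that pre-post data will help to "confirm the effect sizes and sample size for a larger phase 2 randomised controlled trial". It names no return or retention rate. The Design paragraph for Phase 1 counts the 40 at entry only: "We will recruit until we have 40 people who have provided signed consent forms and baseline questionnaires".

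The outcome measures section makes the VGS harm-to-self subscale the primary outcome. In Phase 1 it is scheduled at baseline, 12 weeks and 2 months after treatment.

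For Phase 2, the sample size section requires 50 per group. It raises this to 70 on the basis of the "treatment drop-out rate experienced in" the SGTS programme, about 35%. The analysis section makes the primary analysis intention-to-treat on all available data.

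**The concern.** Leaving therapy and failing to return the outcome are different events. Someone who stops after two sessions may still complete the VGS at 12 weeks, and someone who attends all ten may not. An intention-to-treat analysis needs scores from both.

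The pilot is meant to inform Phase 2, and the feasibility quantities it names describe attendance. The Phase 2 allowance is also an attendance rate. Reporting attendance from Phase 1 would update that rate without showing whether it is the right quantity.

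The stake is Phase 2's precision and, more seriously, its exposure to selective missingness if those who leave therapy are also those who do not answer. The protocol expects about 35% of the pilot sample to have fewer than four sessions, so this group is not small. The Participant commitment section ties two of the fuller questionnaire points to session 4 and session 10, so people who leave early lose those session-linked prompts.

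**Working it through.** **Inputs (protocol, sample size section).** Difference 4.8 points, SD 10.2, r = 0.7, two-sided 5%, power 90%, 50 per group required, about 35% treatment drop-out, 70 per group recruited. From the Phase 1 Design paragraph: n = 40, and about 65% expected to attend four or more sessions.

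**1. Reproduce the 50.** Take one baseline-adjusted follow-up and read r = 0.7 as the baseline to follow-up correlation. The residual variance is 10.2² × (1 − 0.7²) = 104.04 × 0.51 = 53.06. Then n = 2 × (1.960 + 1.282)² × 53.06 / 4.8² = 48.4, so 49 per group against the stated 50. The other bases tried fit less well: unadjusted 95, change score 57, adjusted mean of two follow-ups 35, of three 30.

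**2. Reproduce the 70.** 50 × 1.35 = 67.5, which is close to 70. Dividing instead, 50 / 0.65 = 76.9, so 77. Recruiting 70 to keep 50 therefore allows a loss of 1 − 50/70 = 28.6%, that is, a return of 71.4%.

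**3. Apply the protocol's own 35%, read as missing VGS.** 70 × 0.65 = 45.5 per group. Power = Φ(4.8 / √(2 × 53.06 / n) − 1.96).

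| VGS return | n per group | Power, single follow-up |
|---|---|---|
| 80% | 56 | 93.7% |
| 71.4% | 50 | 90.9% |
| 65% | 45.5 | 88.2% |
| 60% | 42 | 85.5% |
| 50% | 35 | 78.7% |

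**4. Why attendance cannot settle it.** If 65% stay in therapy and every one of them answers, that gives 45.5 per group. The remaining 4.5 must come from the 24.5 who left, which is 18% of them. No named feasibility outcome measures whether they would answer.

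**5. What 40 pilot participants could show.** Exact (Clopper-Pearson) 95% intervals for illustrative counts:

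| VGS returned | Rate | 95% CI |
|---|---|---|
| 22/40 | 55.0% | 38% to 71% (upper limit 70.7%) |
| 23/40 | 57.5% | 41% to 73% |
| 26/40 | 65.0% | 48% to 79% |
| 29/40 | 72.5% | 56% to 85% |
| 34/40 | 85.0% | 70% to 94% |
| 35/40 | 87.5% | 73% to 96% |

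The lower limit clears 71.4% only from 35/40. Every count from 23 to 34 leaves 71.4% inside the interval. The pilot can identify very good or very poor return, and little in between.

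**The case against.** The data will exist. The VGS is scheduled for everyone at 12 weeks and 2 months, willingness to give follow-up data is an inclusion criterion, and half of the $60 voucher is tied to the final follow-up. Using pre-post data to confirm the sample size would show how many people have post-treatment scores, as would the comparison of those below and above four sessions. A completeness table could also sit in a statistical analysis plan. All this is fair, and it means that return could be counted. It does not change the fact that the protocol itself defines feasibility and sizes Phase 2, and uses therapy attendance in both places.

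The power figures above are a worst case. They treat each non-returner as wholly lost on a single follow-up, whereas the stated analysis is a repeated-measures mixed model, with multiple imputation for missing data. On the same inputs, an adjusted mean of two follow-ups with 35 per group gives about 91% power, and of three about 94%, against 79%. That limits the consequence. It does not replace the protocol's calculation, which only the single-follow-up basis reproduces, and neither approach removes bias if return depends on unrecorded gambling outcomes.

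A reader might infer that the pilot could declare Phase 2 feasible on good attendance alone. The protocol does not support that: it has no progression rule or threshold, and speaks only of using what is learned. A reader might also infer that the pilot's return rate should simply replace the 35%. It should not. It would come from one arm, one state and 2 months, with the follow-up contact made by the therapist. Phase 2 is national, has two arms, and runs to 12 months with follow-up by the research assistant.

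**Conclusion.** The point holds in a limited form. The feasibility definition and the Phase 2 allowance both rest on therapy attendance, while the primary analysis depends on VGS return. As written, the pilot is not required to address outcome return or to compare it with the 71.4% that Phase 2 needs.

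The size is moderate: about 88% power instead of 90% if 35% of scores are missing, and below 80% only at about 50% return. These figures assume one baseline-adjusted follow-up, r = 0.7 as the baseline to follow-up correlation, and no information from non-returners. The larger risk, selective missingness among those who leave therapy, cannot be sized from the protocol. The change is worth making before Phase 1 starts, because it uses forms already scheduled.

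**What to change.** - **Hypothesis and Expected outcomes sections:** name as a Phase 1 feasibility outcome the proportion of all 40 enrolled with a VGS at 12 weeks and at the 2-month follow-up, whatever their attendance. Split it by fewer than four versus four or more sessions. Report it with an exact 95% interval beside 71.4%, and state in advance that counts from 23 to 34 of 40 are inconclusive.
- **Sample size section:** express the Phase 2 allowance as missing VGS instead of treatment drop-out, and restate the power or the allowance to match. With 35% missing, either 70 per group is kept with about 88% power on the single-follow-up basis, or 77 per group (154 in total) is needed to retain 50.
- **Use of the pilot rate:** treat it as one input to that allowance and as an optimistic guide, since it stops at 2 months and Phase 2 runs to 12.

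The cost is protocol wording and one extra table, with no added burden on participants. The drawback is an imprecise estimate, roughly plus or minus 15 percentage points at mid-range counts.

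### Phase 1 is single-arm and not hypothesis testing, yet the shared analysis text tests two groups, and its uncontrolled change is to help confirm the Phase 2 effect size

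*Protocol*

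**What the plan says.** - **Purpose (Protocol, Hypothesis, Phase 1 pilot):** "As a pilot study we are not hypothesis testing, instead we are interested in acceptability and feasibility".
- **Design (Pilot trial phase 1 (SA), Design):** "this would be a 12-month single arm trial with all participants being offered CET". The same paragraph predicts attendance among the 40: roughly 5% are expected to come to nothing and 10% to the assessment alone. For the rest it expects "others only 1 assessment and 1-2 therapy sessions (~20%) leaving about 65% who attend 4 or more sessions". It then says: "This provides a naturalistic comparison group ie 35% of the sample who received no or minimal intervention compared to the intervention group (65"%). The 65% are labelled as having had an adequate dose. A per-protocol analysis of people who complete all ten sessions is added, to show what the full dose does.
- **Analysis (How will you measure, manipulate and/or analyse the information collected?), under a label covering both phases:** "The primary analysis will use all available data and follow an intent-to-treat principle to investigate any statistically significant differences in primary and secondary outcomes". The sentence goes on to specify a comparison of two groups over time, and the mixed model has group, time and group-by-time terms. As-treated and per-protocol analyses with inverse probability weighting (IPW) are secondary. Fisher's exact test is planned for the proportion with VGS below 21 at 2, 6 or 12 months.
- **Link to Phase 2 (Expected outcomes):** "Use the learnings and effect size change in the CET group from phase 1 to implement a randomised controlled trial". Phase 1 pre-post data are also to support existing evidence in confirming the effect sizes and sample size of the RCT.

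**The concern.** A trial in which everyone is offered the same treatment has no two groups to compare under intent-to-treat. If the shared analysis text is applied to Phase 1, the analyst must either drop the stated primary analysis or build groups from attendance. People who stay differ from people who leave in ways that may bear on outcome, such as motivation, severity and early response. A difference between them could then be reported as an effect of CET.

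The second issue is the quantity carried forward. A pre-post change in treated people includes regression to the mean and natural recovery as well as any treatment effect. Phase 2 is sized on CET minus an active attention control, which is a different quantity.

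**Working it through.** **1. Which groups could Phase 1 compare?** The Design paragraph gives 5% + 10% + 20% = 35%. Of 40 people that is 2 attending nothing, 4 attending assessment only and 8 attending assessment plus one or two therapy sessions: 14 in all, against 0.65 × 40 = 26. About 12 of the 14 therefore attend at least the assessment, so they are no-or-minimal attenders rather than non-attenders. No other pair of groups is described for Phase 1.

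**2. Is attendance independent of outcome?** The Protocol's own text suggests not. Under Participant commitment, the number of sessions varies with how quickly a person moves through the exposure hierarchy. Session count is thus partly a result of progress. This affects the 14 v 26 contrast, and also the ten-session completers, since someone who progresses quickly may finish in fewer sessions.

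**3. Phase 2 figure, reproduced first.** Inputs from Sample size and statistical or power issues: difference 4.8, SD 10.2, r 0.7, two-sided 5%, power 90%.
- Post scores: 2 × [10.2 × (1.960 + 1.282)/4.8]² = 94.9 per group.
- Baseline-adjusted: 94.9 × (1 − 0.7²) = 48.4, so 49 against the stated 50. This reproduces.

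The Protocol describes 0.7 as a correlation between follow-up measures. Using it as the baseline-to-follow-up correlation is an assumption, though it is the reading that returns the stated 50.

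**4. Precision of 14 v 26, with complete data.** √(1/14 + 1/26) = 0.3315.

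| Analysis | SD used | SE | 95% half-width |
|---|---|---|---|
| Post scores | 10.2 | 3.38 | 6.6 (normal) |
| Change scores | 10.2 × √(2 × 0.3) = 7.90 | 2.62 | 5.3 (t, 38 df) |
| Baseline-adjusted | 10.2 × √0.51 = 7.28 | 2.41 | 4.7 (normal) to 4.9 (t, 38 df) |

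Power to detect 4.8 points is about 29% on post scores and 51% with baseline adjustment.

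**5. Effect of selection (assumed range, not in the Protocol).** Suppose CET has no effect, but attenders have a better prognosis by 0.2, 0.3 or 0.5 SD (2.04, 3.06 or 5.10 points). With SE 3.38, the chance of a significant post-score difference, Φ(b/SE − 1.96) + Φ(−b/SE − 1.96), is about 9%, 15% or 33% instead of 5%.

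**6. Single-arm change.** In all 40 the half-width is t(39) × 7.90/√40 = 2.5 points. In 26 it is t(25) × 7.90/√26 = 3.2 points.

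**7. Pre-post change read as a between-group effect (assumed range).** If 4.8 points were the uncontrolled change and the control arm showed 25% or 50% of it, the between-group difference would be 4.8 × 0.75 = 3.6 or 4.8 × 0.50 = 2.4 points. With 50 per group (baseline-adjusted), power would be about 70% or 38%. Reaching 90% would take 87 or 194 evaluable per group.

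**The case against.** The strongest reply is that the analysis section is RCT text given too wide a label. Its model terms fit a CET arm and a control arm, it never names the 35%/65% split, and the Design paragraph attaches no test to that split. The Hypothesis and Design text point the same way. This stands as a plausible account of how the wording arose, but it does not remove the conflict. The label covers Phase 1, and Fisher's test is listed at 2 months, a visit that What are your outcome measures? gives to Phase 1 and not to Phase 2. The 6-month point fits neither phase, so this evidence is suggestive only.

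IPW is a real safeguard for attendance-based contrasts if they are treated as secondary. It covers only measured predictors of attendance, has little to work with in 40 people, and is not planned for the primary analysis.

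A reader might infer two stronger points that the Protocol does not support:
- **That the pilot is committed to publishing a p-value for treated against untreated people as evidence of efficacy.** No sentence says so, and most of the comparison group receives some contact.
- **That Phase 2 is sized from the pilot's pre-post change.** The 140 is already derived from a between-group 4.8 points and SD 10.2. Phase 1 only helps to confirm it alongside other evidence, and no re-sizing rule is given.

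Nor can the Phase 1 interval be called clearly wider than the target: that holds for change scores but is not settled with baseline adjustment. A wide interval is in any case normal in a pilot of 40.

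**Conclusion.** The point holds as an internal contradiction with a foreseeable misuse. As labelled, the stated primary analysis cannot be carried out in Phase 1, because no groups are assigned. The only available pair is defined after enrolment by behaviour, and neither that contrast nor the ten-session analysis isolates the effect of CET. Precision is about the size of the Phase 2 target (half-width 4.7 to 5.3 points against 4.8) before any selection bias. This rests on the predicted 35/65 split, complete data, SD 10.2 and 0.7 taken as the baseline-to-follow-up correlation. The illustrations of selection and of control-arm improvement use assumed ranges.

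The feed into Phase 2 is a secondary weakness: an uncontrolled change is not the quantity on which the RCT is powered, but it is not the sole basis for the sample size. The randomised comparison itself is unaffected. Severity: should-fix.

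**What to change.** 1. In the analysis section, limit the between-group primary analysis, the group and group-by-time terms and Fisher's test to Phase 2.
2. For Phase 1, report recruitment and completion proportions, and VGS change from baseline in all 40, each with a 95% CI.
3. In the Design paragraph, present outcomes by sessions attended, including ten-session completers, as exploratory and descriptive. Remove the descriptions of a comparison group and of a full-dose effect.
4. In Expected outcomes, carry only SD, baseline-to-follow-up correlation, retention and attendance from Phase 1 into the Phase 2 sample size. Keep the 4.8-point between-group target, and state that the pre-post change does not estimate it.

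The cost is protocol wording and the loss of a headline dose comparison that could not have been interpreted causally. No extra participants or data are needed.
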